6.1 Randomization and blinding

Eligible patients will be randomly allocated to receive either susceptibility-based tailored therapy (tailored therapy) or empirical bismuth quadruple therapy (empirical therapy) in a 3:1 ratio. An independent statistician at Shanghai Jiao Tong University College of Basic Medical Sciences generates the computerized random number sequence and used a permuted block randomization with a block size of eight. All investigators is masked to the randomization sequence. Allocation is concealed in an opaque envelope until the intervention was assigned. Envelopes will be kept at Renji Hospital. After the written informed consents would be obtained from eligible patients, the independent research assistant will open envelopes by randomization sequence and telephone study staff to give them each patient's treatment allocation. This study is an open-labeled trial and patients are not blinded. The technicians, who perform the H. pylori tests (rapid urease test, culture, antimicrobial susceptibility testing, and urea breath test) or fill in the questionnaires, will be blinded to treatment allocation.

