10.1 Sample size

Assuming 96.5% eradication rate of tailored therapy in our trial, 88.9% eradication rate of empirical therapy, a superiority margin of >0 , a power of 80%, an alpha of 0.05 (one-sided), a ratio of 3:1, at least 260 subjects in susceptibility-based therapy and 87 subjects in empirical therapy will be required to show superiority of susceptibility-based therapy over empirical therapy on the basis of H. pylori eradication rate. Taking into consideration of 10% lost to follow-up, at least 382 participants (286 for tailored therapy and 96 for empiric therapy) is expected to be recruited for the study.

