4.3 Testing the superiority of the tailored therapy

Testing the superiority of tailored therapy group to empiric therapy group will be performed in the ITT and PP analysis populations using hypothesis testing (one-sided Z test) and derivation of a two-sided 95% confidence interval (CI) of difference based on *H. pylori* eradication rate. If p-value of the testing less than 0.025 and the lower bound of the 95% CI greater than zero, superiority of susceptibility-based therapy over empirical therapy could be concluded.

5. Evaluation of secondary outcomes

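### The stated 80% power is computed at one-sided 0.05, but success requires one-sided 0.025; under that rule the 3:1 design has about 76% power or less, and the unexplained 3:1 ratio accounts for part of the gap

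*Combined protocol and SAP*

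**What the plan says.** Final Protocol 10.1, repeated in Final SAP section 1, assumes 96.5% eradication on tailored therapy and "88.9% eradication rate of empirical therapy", with "a superiority margin of >0" and "a power of 80%, an alpha of 0.05 (one-sided), a ratio of 3:1". It concludes that "at least 260 subjects in susceptibility-based therapy and 87 subjects in empirical therapy will be required", then adds 10% for loss to follow-up to reach 286 + 96 = 382.

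Final Protocol 6.1 allocates patients to tailored or "empirical bismuth quadruple therapy (empirical therapy) in a 3:1 ratio", in permuted blocks of eight. Neither 6.1 nor 10.1 explains the ratio.

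Final Protocol 10.3 and Final SAP 4.3 set the success rule: a one-sided Z test with "p-value of the testing less than 0.025 and the lower bound of the 95% CI greater than zero". They do not say whether the Z test uses a pooled variance, or how the interval is calculated. Final Protocol 10.2 and Final SAP 2.1 keep every randomised patient in the ITT set and count a missing breath test as failure.

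**The concern.** Two features of the plan work against its 80% claim.

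First, the sample size uses twice the one-sided error rate that the success rule allows, so the quoted power belongs to a test that the trial will not use.

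Second, at the planned rates the per-patient variance is 0.965 × 0.035 = 0.034 on tailored therapy and 0.889 × 0.111 = 0.099 on empirical therapy, a ratio of about 2.9. The noisier arm receives 96/382 = 25% of patients. For comparing two proportions this is the inefficient direction.

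At stake is a trial that misses a real benefit of the planned size more often than its protocol tells investigators and ethics committees.

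**Working it through.** **Inputs.** pT = 0.965, pE = 0.889, difference 0.076, k = 3, 80% power (Final Protocol 10.1); decision at one-sided 0.025 plus a 95% CI (Final SAP 4.3).

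**The plan's own figure.** With pooled variance and no continuity correction,

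nE = [zα √(p̄(1−p̄)(1+1/k)) + 0.8416 √(pE(1−pE) + pT(1−pT)/k)]² / (pT−pE)²,

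where p̄ = (0.889 + 3 × 0.965)/4 = 0.946.

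- At one-sided 0.05: (1.645 × 0.2610 + 0.8416 × 0.3316)² / 0.005776 = (0.4293 + 0.2791)² / 0.005776 = 86.9. That gives 87 empirical and 261 tailored, against the stated 87 and 260.
- Multiplying 260 and 87 by 1.1 gives 286 and 95.7, the stated 286 and 96.

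The plan's arithmetic is therefore right for the error rate it names.

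**The same formula at the success rule.** At one-sided 0.025: (0.5115 + 0.2791)² / 0.005776 = 108.2. That is 109 + 327 = 436 evaluable patients, not 347.

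**Power by formula at 3:1 and 0.025.**

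- 286/96, pooled Z: (0.076 − 1.960 × 0.02668)/0.03385 = 0.700, so 75.8%.
- 260/87, pooled Z: 72.4%.
- 286/96, Wald lower limit above zero: 0.076/0.03385 − 1.960 = 0.285, so 61.2%.

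**Exact power.** Both binomial distributions were enumerated in full at the planned rates. The rule needs both conditions and the CI method is not named, so two intervals are shown, each combined with the pooled Z test.

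| Analysed | Split | Z alone | Z and Wald CI | Z and Newcombe CI |
|---|---|---|---|---|
| 382, 3:1 | 286/96 | 76.4% | 65.0% | 75.6% |
| 347, 3:1 | 260/87 | 72.9% | 59.3% | 71.6% |
| 382, 1:1 | 191/191 | 83.9% | 83.9% | 83.1% |
| 344, 1:1 | 172/172 | 79.5% | 79.5% | 78.7% |

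The last row removes 10% of 382 (382 × 0.9 = 343.8).

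**How much is due to each cause.** Take Z alone at 286/96. Moving from one-sided 0.05 to 0.025 lowers exact power from 83.9% to 76.4%. At 0.025, moving from 3:1 to 1:1 raises it from 76.4% to 83.9%. Each step is about 7.5 points. Under the joint rule the gap between the ratios is 83.1 − 75.6 = 7.5 points with Newcombe and 83.9 − 65.0 = 18.9 with Wald. By the pooled formula, 1:1 needs 288 evaluable patients against 348 at one-sided 0.05, and 366 against 436 at 0.025. The inefficiency is therefore present at either error rate.

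**Losses scored as failures.** If 10% are lost in each arm on top of the planned rates, the ITT rates become 0.965 × 0.9 = 86.9% and 0.889 × 0.9 = 80.0%. Exact power at 382 is then 30.1% (Wald) to 37.9% at 3:1 and 43.8% at 1:1.

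**The case against.** **The ratio is not the error.** The 3:1 split was an input to the sample-size formula, and at one-sided 0.05 the design reaches 80% (80.0% by formula and 80.7% exact at 260/87, Z alone). The stated power fails because of the mismatched error rates. This stands: rebalancing would offset the mismatch without reconciling it.

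**Allocation is a design preference.** The tailored arm splits into four regimens by resistance pattern (Final Protocol 6.2), and Final SAP Table 4 has a row for each. More tailored patients make those single-arm rates more precise. The documents do not give this as their reason, but it is a reasonable one. Table 4 also compares the arms within each row, however, and there the 96 controls are spread thinly.

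**Stronger readings that a reader might infer:**

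- *Rebalancing restores 80% at no cost.* At 1:1 this needs all 382 patients observed at the planned rates. The plan allows for 10% loss, and with 344 evaluable 1:1 falls just short.
- *Any more balanced ratio would do.* With all 382 analysed and a Wald interval, 2:1 (255/127) reaches only 74.9%. A 3:2 split is borderline at 80.6% and does not fit blocks of eight.
- *3:1 inflates the false-positive rate.* The pooled Z test alone does run at 2.9 to 3.5% for common rates between 88.9% and 96.5%. But the plan also requires the CI condition. With a Wald interval the joint rule is conservative at 3:1 (0.9 to 1.6%); with Newcombe it is about 2.8 to 3.0%. The CI method is not named, so the documents do not support a general claim of inflation.

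**Conclusion.** The 80% power statement is wrong as written for the success rule in the plan. With all 382 analysed, the 3:1 design has about 76% power (pooled Z alone or with a Newcombe interval) or 65% (Wald). With 347 evaluable it has about 72 to 73%, or 59%. The error-rate mismatch and the 3:1 ratio both contribute.

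At fixed size, 1:1 had more power than 3:1 in every case checked, but whether it reaches 80% is conditional. These figures rest on the planned 96.5% and 88.9% and on an assumed pooled Z test; the range reflects the unnamed interval. If the planned rates exclude losses that are then scored as failures, power is far below 80% at either ratio.

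The validity of the primary comparison is not in question. This point concerns its stated power and the efficiency of the allocation.

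**What to change.** 1. In Final Protocol 10.1 and Final SAP section 1, restate power at the one-sided 0.025 rule. In Final Protocol 10.3 and Final SAP 4.3, name the variance used in the Z test and the CI method. Say whether 96.5% and 88.9% already count losses as failures. This costs only wording.
2. Give the reason for 3:1 or, before recruitment, consider 1:1 at the same 382 (191/191). Blocks of eight still work, as 4 + 4 instead of 6 + 2. This needs a new randomisation list and edits to Final Protocol 6.1 and 10.1 and Final SAP section 1, with no extra patients.
3. Weigh the trade-off openly. Tailored patients fall from 286 to 191, a third fewer, so eradication rates within each tailored regimen become less precise, while the between-arm comparison gains controls.

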8.3 Serious adverse event (SAE)

(1)The judgments of SAE:

- Death, Life-threatening,
- Leading to hospitalization or prolong hospitalization time,
- Permanent or severe disability,
- Congenital Anomaly/Birth Defect.

(2)SAE report system:

Principal investigator and the hospital ethics committee should be reported and SAE report form should be filled in within 24 hours by phone no matter whether any kinds of SAE are related with the drug in 30 days after the treatment. And the form should be reported to national drug administration in time by principal investigator. SAE should be promptly handled, closely tracked until it is properly solved.

Contact method:

1) Contact persons: [name] [name]

2) SFDA Safety Supervision

9. Outcome Measures

9.1 Primary Outcome Measure:

1. Helicobacter pylori eradication rate

Six weeks after completion of therapy, H. pylori eradication success is defined as negative result from urea breath test (<4%). If patients would be lost to follow-up urea breath testing, they will be scored as treatment failures in the ITT analysis. The eradication rate is defined as the number of patients who successful eradicate *H. pylori* divided by the total number of population for analysis.

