10.2 Statistical Analysis Data

Intention--to-treat (ITT) Analysis population: According to the Intention-to-treat principle: All randomized patients will be included in the ITT analysis. Patients who did not return for a follow-up 13C-UBT will be recorded as treatment failures.

Per-protocol (PP) analysis population: All individuals who violated the study protocol, such as patients not taking at least 80% of treatment drugs, or with unknown post-treatment H. pylori status will be excluded from the PP analysis.

Safety analysis population: The patients with missing safety data in ITT population will be excluded from the safety analysis.

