10.3 Statistical methods

Comparative superiority of the two groups was assessed through hypothesis testing (one-sided Z test) and derivation of a two-sided 95% confidence interval (CI) of difference based on H. pylori eradication rate. If p-value of the testing less than 0.025 and the lower bound of the 95% CI greater than zero, superiority of susceptibility-based therapy over empirical therapy could be concluded.

Between-group differences were evaluated using Student's t-test for continuous variables and Pearson's χ^2 /corrected χ^2 or Fisher's exact test for categorical variables, as appropriate. All p-values were two-sided except the testing of superiority, and were considered statistically significant if p-value less than 0.05.

Subgroup analyses of eradication efficacy were performed based on the results of antibiotic susceptibility test and compliance assessment.

11 Ethical principles

The study is registered in ClinicalTrials.gov. The study protocol is approved by the Ethics Committee at all institutions, and the study will be performed according to good clinical practice and the Declaration of Helsinki.

Before each patient is selected into the study, the physician of the study have the responsibility to tell patients or their designated agents the purpose, process, completion and comprehensively introduce possible adverse reactions, risks to bear, possible benefits and other information all-round and detailed, making the patients know their rights. We are ordered to inform the patients of having the right to decide whether to participate in the study, as well as the right to withdraw the study at any time without any discrimination. The patients or their legal representatives should sign the informed consent after carefully reading and fully understanding, and retain the signature page of the copy.

12 References

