Subjects without AEs

Subjects with AEs

Total

AE, adverse event.

Final Statistical Analysis Plan

This statistical analysis plan includes the details of study sample size calculation and statistical methods for analysis of outcomes and safety.

Table of Contents

1. Sample size estimation	68
2. Definition of populations for analysis	68
3. Evaluation of baseline characteristics	68
4. Evaluation of primary outcomes	70
5. Evaluation of secondary outcomes	70
6. Additional analyses	72
7. Table Design	73

1. Sample size estimation

Assuming 96.5% eradication rate of susceptibility-based therapy in our trial, 88.9% eradication rate of empirical therapy, a superiority margin of >0 , a power of 80%, an alpha of 0.05 (one-sided), a ratio of 3:1, at least 260 subjects in susceptibility-based therapy and 87 subjects in empirical therapy will be required to show superiority of susceptibility-based therapy over empirical therapy on the basis of H. pylori eradication rate. Taking into consideration of 10% lost to follow-up, at least 382 participants (286 for tailored therapy and 96 for empiric therapy) is expected to be recruited for the study.

2. Definition of populations for analysis

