2.2 Per-protocol (PP) analysis population

All individuals who violated the study protocol, such as patients not taking at least 80% of treatment drugs, or with unknown post-treatment H. pylori status will be excluded from the PP analysis.

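### The 10% loss allowance keeps 80% power only in a set that drops lost patients; if 96.5% and 88.9% are rates among breath-tested patients, ITT power at 10% loss is about 49% (one-sided 0.05)

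*Combined protocol and SAP*

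**What the plan says.** Section 10.1 of the final protocol and section 1 of the final SAP use the same inputs: "Assuming 96.5% eradication rate of susceptibility-based therapy in our trial, 88.9% eradication rate of empirical therapy", margin zero, one-sided alpha 0.05, power 80% and 3:1 allocation. These give 260 tailored and 87 empirical patients. The allowance follows: "Taking into consideration of 10% lost to follow-up, at least 382 participants (286 for tailored therapy and 96 for empiric therapy".

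The ITT rule is in protocol 10.2 and SAP 2.1: "Patients who did not return for a follow-up 13C-UBT will be recorded as treatment failures". Protocol 9.1 says the same of patients lost before the breath test: "they will be scored as treatment failures in the ITT analysis". Only the PP set removes them, and it removes others too; SAP 2.2 says that "patients not taking at least 80% of treatment drugs, or with unknown post-treatment H. pylori status will be excluded".

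SAP 4.3 uses both sets: "Testing the superiority of tailored therapy group to empiric therapy group will be performed in the ITT and PP analysis populations". The success rule in protocol 10.3 and SAP 4.3 has two parts: "If p-value of the testing less than 0.025 and the lower bound of the 95% CI greater than zero". No CI method is named. No section says which analysis set the assumed rates describe, and none lowers them for losses counted as failures.

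**The concern.** A sample-size allowance for loss works when lost patients drop out of the analysis and are replaced. Under this ITT rule they remain in the denominator with a failed outcome. Equal loss in the two arms then multiplies both success rates by the same factor below one. The difference shrinks, and both rates move towards the middle of the scale, where the variance is larger. Ten per cent more patients does not offset this.

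The only power figure in the plan is 80%, so a reader has no other value to attach to either superiority test. If ITT power is in fact nearer one half, a non-significant ITT result is weaker evidence against tailored therapy than the stated power suggests.

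**Working it through.** **Inputs.** From protocol 10.1 and SAP 1: success rates 0.965 (tailored) and 0.889 (empirical); 260/87 before and 286/96 after the allowance; one-sided alpha 0.05. From protocol 9.1 and 10.2: loss counts as failure in ITT.

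**Formula (pooled Z test).** With difference d, SE0 the standard error under the pooled rate and SE1 the unpooled standard error,

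power = Φ((d − z·SE0)/SE1), with z = 1.645 at one-sided 0.05.

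**1. The plan's own figure.** At 260/87: d = 0.076, SE0 = 0.02801, SE1 = 0.03555. (0.076 − 1.645 × 0.02801)/0.03555 = 0.842, so power is 80.0%. The stated size reproduces.

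**2. The allowance.** 260 × 1.1 = 286; 87 × 1.1 = 95.7, rounded to 96; total 382.

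**3. Set that excludes only lost patients.** 10% off 286/96 leaves about 257/86, where power is 79.7%. The allowance does its job here.

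**4. ITT, reading (a): 96.5% and 88.9% are rates among breath-tested patients.** Assume loss L is equal in both arms and unrelated to outcome. The ITT rates are then 0.965(1 − L) and 0.889(1 − L), at 286/96. For L = 10%: 0.8685 and 0.8001, d = 0.0684, SE0 = 0.04197, SE1 = 0.04545. (0.0684 − 1.645 × 0.04197)/0.04545 = −0.014, so power is 49.4%. Exact binomial enumeration of the same test gives 48.7%.

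| Loss per arm | ITT rates | Power, one-sided 0.05 |
|---|---|---|
| 0% | 96.5% v 88.9% | 82.9% |
| 2% | 94.6% v 87.1% | 74.3% |
| 5% | 91.7% v 84.5% | 63.2% |
| 10% | 86.9% v 80.0% | 49.4% |

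Under these assumptions ITT power reaches 80% only if loss is below about 0.7% per arm, and it drops under 50% above about 9.8%. Restoring 80% by size alone would take about 460, 632 or 944 patients at 2%, 5% or 10% loss.

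**5. ITT, reading (b): the rates are already ITT rates.** Power at 286/96 is 82.9%. But the tailored ITT rate cannot exceed 1 − L. At 2% loss, 96.5% implies 0.965/0.98 = 98.5% among tested patients; at 3.5% loss it implies 0.965/0.965 = 100%. So the rate allows at most 0.035 × 286 = 10 losses. With 10% lost the ITT rate could not be above 90%.

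**6. Full success rule.** Exact enumeration of both conditions (pooled Z p < 0.025 and lower 95% limit above zero), under the assumptions of step 4:

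| Set | Wald CI | Newcombe CI |
|---|---|---|
| ITT, 0% loss | 65% | 76% |
| ITT, 2% loss | 53% | 64% |
| ITT, 5% loss | 42% | 52% |
| ITT, 10% loss | 30% | 38% |
| 257/86, lost patients excluded | 59% | 71% |

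Part of the fall in this table comes from the stricter threshold and the CI method, not from loss. The mismatch between alpha 0.05 and the 0.025 rule is a separate issue.

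**7. PP set.** If a further 5% were excluded for under-dosing or other violations (an assumed figure), 243/82 would remain, with power 78% at 0.05.

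**The case against.** The strongest reply is that 49% sits at one corner. It needs the rates to be those of breath-tested patients, the whole allowance to be used, and equal loss unrelated to outcome. Ten per cent is a planning allowance, not a forecast. This stands, which is why the result is given as a range; even 2% loss brings ITT power to 74%.

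Equal loss is also not guaranteed in an open-label trial whose arms receive different regimens. With the same formula at 286/96 and one-sided 0.05, illustrative losses of 8% tailored and 12% empirical give 80%; 5% and 10% give 90%; 10% and 5% give 15%. So the 0.7% and 9.8% thresholds hold for equal loss only. Equal loss is nevertheless what the plan's own uniform 10% implies, and power gained from heavier loss in the empirical arm would partly reflect loss rather than efficacy.

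The final documents do not name ITT as primary; only the superseded protocol does. On that view the allowance is coherent for a set that drops lost patients, and 260/87, 286/96 and 80% all reproduce. That is correct. The fault is that 80% is stated without a set, while SAP 4.3 also tests ITT.

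Finally, once data exist, the confidence interval shows how informative a non-significant result is. True, but it does not make the stated design power right for the ITT test. The shortfall from further PP exclusions, 80% to 78%, is small.

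**Conclusion.** The concern holds. The arithmetic from 260/87 to 286/96 reproduces, but it protects 80% power (one-sided 0.05) only in a set that excludes lost patients and nobody else. For the ITT test the figure is unsupported under one reading and at odds with the plan's own 10% under the other.

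Reading (a) is the more natural, because a 96.5% ITT rate cannot coexist with 10% of tailored patients scored as failures. ITT power then runs from 74% at 2% loss to 49% at 10%, given equal loss unrelated to outcome, and is lower under the full success rule. The algebra is firm; the actual ITT power depends on a loss rate and an analysis set that the documents leave open. This should be fixed.

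**What to change.** In protocol 10.1 and SAP section 1:

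1. State which analysis set 96.5% and 88.9% describe.
2. Give ITT power with loss counted as failure at 2%, 5% and 10% loss, at the planned one-sided 0.05 and under the full success rule, and name the CI method. Label any 0.025 figure that comes from the pooled Z test alone as such: 65%, 52% and 38% for ITT, and 72% for 257/86. State the equal-loss assumption beside the table; a row with unequal loss would help.
3. Attach 80% only to the set that excludes lost patients, at one-sided 0.05, and say that no allowance is made for other PP exclusions.

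The cost is a few sentences and a small table, and the stated ITT power becomes less favourable. No change to sample size, analysis sets or test is proposed.

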10.2 Statistical Analysis Data

Intention--to-treat (ITT) Analysis population: According to the Intention-to-treat principle: All randomized patients will be included in the ITT analysis. Patients who did not return for a follow-up 13C-UBT will be recorded as treatment failures.

Per-protocol (PP) analysis population: All individuals who violated the study protocol, such as patients not taking at least 80% of treatment drugs, or with unknown post-treatment H. pylori status will be excluded from the PP analysis.

Safety analysis population: The patients with missing safety data in ITT population will be excluded from the safety analysis.

